D. DESIGN AND METHODS

We will enroll 30 subjects in this double-blind sham control study. Fifteen subjects will undergo sham stimulation for 4 weeks while the other 15 will have auricular microstimulation for 8 weeks. Then, the 15 subjects who were in the sham group will undergo stimulation for 4 weeks.

We will measure vagal modulation supine and standing utilizing heart rate variability, measure cytokines and mitochondrial bioenergetics through a Seahorse analysis at week 0, 4 and 8.

Inclusion Criteria:

- Female patients 12 18 years old with chronic idiopathic nausea, functional abdominal pain, dyspepsia and/or irritable bowel syndrome.
- English speaking

Exclusion Criteria:

- Patients who are unable to stand upright during the heart rate variability recording
- Patients with a known bleeding disorder
- Patients with swollen, infected, inflamed, or other skin eruptions on outer ear
- Patients with epilepsy
- Patients with any implanted cardiac pacemaker or defibrillator
- Patients with serious arterial circulatory problems in the lower limbs
- Patients with abdominal or inguinal hernia

- Patients who are pregnant
- Any unstable medical condition, such as renal disease, uncontrolled diabetes, etc.
- Requires new medication during the 8 weeks of the study that may affect the gastrointestinal symptoms, vagal modulation or immune response.
- Inability to answer questionnaires or report pain in a 0-10 visual analog scale.

Week 0 – Visit 1 (Enrollment)

A member of the research team will approach the patient and his/her legal guardian during his/her visit to the Functional and Gastrointestinal Disorders Clinic. If the patient and his/her guardian are unable to complete consent documents during the visit, the researcher may collect consent over the phone or at the study baseline visit in the Pediatric Translational Research Unit (TRU), prior to starting study procedures.

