Study participants will complete the following study questionnaires: Functional Disability Inventory-Child and Adolescents Form, Symptom Intensity Questionnaire, Pain Catastrophizing Scale and Revised Child Anxiety and Depression Scale. The participant's parent will also complete the Functional Disability Inventory-Parent Form. The participant will also be asked to complete the TENS Unit Daily Recording Diary to document when the device was used. A member of the research team will review the questionnaire instructions with the study participants and will advise them that they are allowed to skip any question that they are not comfortable answering. The researcher will review the questionnaires for any missed responses and will confirm with the participant if the question(s) was intentionally skipped.

Subjects will be randomized to 2 groups: a) group 1: 15 females who will only undergo active auricular TENS unit stimulation for the 8 weeks. B) Group 2: 15 females who will undergo for the first 4 weeks sham (tactile) stimulation, and the 4 weeks of active stimulation. The active settings for the TENS unit is micro mode, pulse width: 50 millisecond (ms), a frequency of 10 Hertz (hz), and intensity at sub-sensory to minimally perceived threshold. The study investigating physician will place the first TENS unit to the participant's inner part of each ear (conchae) using a clip that is provided. The investigator will train the participant on how to place the unit at home. Subjects will be asked to use the unit for at least 1 hour, twice a day. The patient will determine what time during the day that they will utilize the unit, depending on their schedule. To document the placement and the time of day that the unit is use, a data collection form will be provided. A study team member's contact

information will also be provided if the patient has any questions or concerns. A study team member will contact the patient 2 times each month as a check in and reminder. The sham stimulation will be done with non-conductive cotton cushion applied to the electrodes and the TENS unit set at an intensity of 0.02mA. The investigator and performing research coordinator will be blinded to the stimulation mode. It is possible and permitted that the performing research coordinator will become aware of which group the subject is in when checking in on the subject.

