Participants will receive a \$20 check following the completion of each of the first study visit, a \$20 check after completing the second visit and \$30 for completing the final study visit. All checks will be written in the participant's name.

E. TOTAL NUMBER OF HUMAN RESEARCH PARTICIPANTS PROPOSED FOR THIS STUDY AT THIS SITE AND GLOBALLY. WHAT ARE THESE NUMBERS BASED ON?

For this pilot protocol, we will enroll 30 subjects from the Functional and Gastrointestinal Disorders Clinics in Children's Hospital of Wisconsin. The PI and her nurse practitioner see 16 patients with FGID per week. We have been performing many studies in our clinic and patients are usually very eager to participate; therefore, we are not concerned about the feasibility of completing this pilot study in 1 year. Furthermore, the study was designed so that every subject gets the active intervention, in part to increase enrollment and retention.

F. DRUGS OR PROCEDURES

MD Assessment Form

Investigating physicians will perform a brief medical assessment with the participant to confirm study eligibility. This assessment includes a detailed history of gastrointestinal symptoms such as nausea, vomiting, abdominal pain, location of pain, duration & frequency of symptoms, bowel movements – frequency and consistency. In addition, this form will be used to evaluate non-gastrointestinal comorbid burden such as abdominal migraine and cyclic vomiting syndrome, temporomandibular joint disorder (TMJ), chronic fatigue, urinary symptoms, pelvic pain (including dysmenorrhea, endometriosis etc.), other chronic pain types, Raynaud's syndrome, syncope, postural tachycardia syndrome, chronic nausea or vomiting, complex regional pain syndrome, panic disorder, PTSD, anxiety and affective disorders and fibromyalgia (original criteria), evaluated by assessing 18 tender points described by the American College of Rheumatology³⁴. Each symptom will be ranked as not present, possible, probable or definite based on the appropriate consensus criteria.

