Blinding methodology: Patients will be informed that we are comparing 2 methods of ear stimulation, tactile and active. Both methods will be explained (either setting the machine at 0.02mA and using dry, nonconductive pads, or moving the device up until the stimulus is just experienced and then lowering until it is no longer experienced). Because the first stimulus is tactile, we will not use the word "sham" or "placebo", as we do not know that a tactile stimulus does not have some effect. In fact, ear piercings are popular for these symptoms. After both methods are explained the subject will demonstrate understanding of each. Once home, the patient will open a sealed envelope that was prepared by an independent research coordinator, and unknown to the investigator or the performing research coordinator, that instructs them as to which method to utilize. Only the independent research coordinator and the biostatistician will know the arm assigned. At the participant's Week 4 visit, the researcher will collect the previously used TENS unit device. The research coordinator will then provide all participants with another auricular device and letter which will include instructions on how to use the device during the remaining 4 weeks. It is remotely possible that some subjects will realize that the tactile form of the stimulation with dry cotton pads is actually a **sham** version of the stimulator. We think this is unlikely for 2 reasons. First, tactile stimulation of the ear is in fact sometimes referenced in the popular literature as a treatment (though this has not been formally tested). Second, neither version of the stimulator produces any conscious electrical sensation, so they will be quite comparable from an experiential perspective. In addition, the fact that tactile stimulation may have some effect will not alter the fundamental goal of this protocol, as we will be looking at the difference between the tactile and the electrical stimulating version. It is possible and permitted that the participant and the research team will become aware of which group the participant was initially assigned at the Week 4 visit.

TENS unit and Auricular Clip Placement

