Patients who turn 18 years of age while participating in this study will be re-consented either in clinic at a routine visit or over the phone. If a participant is re-consented over the phone, a member of the research team

will first mail the "Letter to Reconsent Enrolled Participants" and a blank Consent/HIPAA form to the participant's address listed in the participant's medical record. A member of the research team will call the participant to complete the informed consent discussion over the phone. Once the participant signs the Consent/HIPAA form, he/she will mail it back to the research team member who completed the discussion and he/she will complete the corresponding signature portion. A completed copy will be mailed to the participant and a copy will be uploaded into the participant's medical record. The researcher will document this process on the informed consent discussion form which will be filed with consent form.

O. PROCEDURES TO BE EMPLOYED IN ANALYZING DATA AND THE ANTICIPATED SIGNIFICANCE OF THE PROPOSED STUDY

Data Management and Analysis The data gathered will be entered into RedCap data system with each ID having a unique identifier for each participant. REDCap is a secure, web-based application for building and managing online databases. All data will be de-identified, and samples will only have a unique identifier that will link the unique identifier with the patient's name.

Missing Data: Every effort will be made to avoid missing data. Using logistic regression, the pattern of missing data will be explored. Assuming the data are missing at random (MAR) multiple imputations for items will be used.

Randomization: we will randomize using Piantadosi randomization in blocks of 10. The sample size in this pilot study is small and it would likely result in bad imbalance of the two groups.

Data analysis overview: Summary statistics, such as mean, median, standard deviation, range and correlation will be used as a first step to examine data. To satisfy parametric assumptions, we may perform transformations with justifications if possible and otherwise use non-parametric tests. Statistical software employed for data analysis will be: Cytel StatXact, SAS version 9.4, SPSS Version 24. The power calculation was made using PASS 15.

Heart Rate Variability

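### A fixed, published block size of 10, with recruiting staff permitted to learn earlier arms, lets a few later allocations be deduced despite the sealed envelope

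*Combined protocol and SAP*

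**What the plan says.** **Randomization.** Section O (Randomization) states "we will randomize using Piantadosi randomization in blocks of 10" and gives imbalance in a small sample as the worry. It mentions no variation in block size and no stratification, and it does not define the named method. Section D gives the totals: "We will enroll 30 subjects in this double-blind sham control study" and "Fifteen subjects will undergo sham stimulation for 4 weeks while the other 15 will have auricular microstimulation for 8 weeks".

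**Concealment.** Section F (Blinding methodology) has an independent coordinator prepare a sealed envelope that the patient opens at home. It says that only this coordinator and the biostatistician know the arm.

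**Permitted disclosure.** Other text departs from that.
- Section D, Week 0: "It is possible and permitted that the performing research coordinator will become aware of which group the subject is in when checking in". On how often: "A study team member will contact the patient 2 times each month as a check in and reminder".
- Section F permits that "the research team will become aware of which group the participant was initially assigned at the Week 4 visit".
- Section D, Week 4, has the study investigator give intensity instructions specifically to those who had been on sham. Section F instead has the coordinator hand every participant a new device and a letter.

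**Who recruits.** Under sections D and N, members of the research team and study investigators approach and consent patients. Section E expects a short study: "we are not concerned about the feasibility of completing this pilot study in 1 year".

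**The concern.** An envelope protects the next allocation only if that allocation cannot be worked out from earlier ones. Here the block length is printed in the document the team works from, recruitment is at a single clinic, and the people permitted to learn past arms belong to the team that decides whom to approach and when. If five participants in a block are known to be on one arm, everyone still to enter that block is on the other.

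The stake is selection at entry. With 15 per arm, one steered enrolment is 1/15 = 6.7% of an arm. The clinical measures (FDI, symptom intensity) are largely self-rated. The HRV and cytokine measures are not, but selection acts through who enters each arm, so objective measurement does not fully protect against it.

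**Working it through.** **Inputs.** Block size 10 (section O); 30 participants, 15 per arm (section D); check-ins twice a month (section D); disclosure at Week 4 (sections D and F); one year (section E). Three assumptions are mine: a 5:5 split in each block, 30 evenly spaced enrolments over 52 weeks, and a first check-in about two weeks after enrolment.

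**The plan's own figure.** 30/10 = 3 blocks and 3 × 5 = 15 per arm, so the stated split is reproduced.

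**How many recent arms are still unknown (L).** Spacing is 52/30 = 1.73 weeks. At a two-week reveal, the participant enrolled 1.73 weeks ago is unknown and the one enrolled 3.47 weeks ago is known, so L = 1. At a Week 4 reveal, those at 1.73 and 3.47 weeks are unknown and the one at 5.2 weeks is known, so L = 2. If the last participant must finish 8 weeks of follow-up within the year, spacing is 44/30 = 1.47 weeks and L is again 1 and 2.

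**Deducible allocations, fixed blocks, every arm learned.** An allocation is certain when it, the L before it and everything after it in the block all belong to one arm. The chance that the last m places in a block share an arm is 2·C(10−m,5)/C(10,5), with C(10,5) = 252:

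| m | 1 | 2 | 3 | 4 | 5 |
|---|---|---|---|---|---|
| probability | 1 | 0.4444 | 0.1667 | 0.0476 | 0.0079 |

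The expected number per block is the sum from m = L+1 to 5. Multiply by 3 for the trial. The chance p of at least one in a block is the entry at m = L+1, and for the trial it is 1 − (1 − p)³.

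| L | per block | of 30 | chance of at least one |
|---|---|---|---|
| 0 | 1.667 | 5.0 | 100% |
| 1 | 0.667 | 2.0 | 83% |
| 2 | 0.222 | 0.67 | 42% |
| 3 | 0.056 | 0.17 | 14% |

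**Sensitivity.**
- Enrolment times scattered at random over 52 weeks (simulation): 2.4 (89%) for a two-week reveal and 1.1 (59%) for Week 4.
- Enrolment over 26 weeks with learning at Week 4: 0.02 if evenly spaced, 0.2 if scattered.
- Only a share q of arms learned: all five of the completed arm must be known, so each expectation is multiplied by q⁵. For q = 0.5 the factor is 1/32, giving 2.0/32 = 0.06 at L = 1 and 0.67/32 = 0.02 at L = 2. With scattered enrolment times the simulated value for a two-week reveal is 0.07.

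**Varying sizes, example 4, 6, 8 and 12 in random order.** Staff do not know where blocks end, but they do know the total is 15:15, so the end of the last block can still be deduced. Each size is last with probability 1/4. For a block of size 2h the L = 0 expectation is 2h/(h+1), so the average is (1.333 + 1.500 + 1.600 + 1.714)/4 = 1.54.
- L = 1: subtract the m = 1 term, which is 1. This leaves 0.54.
- L = 2: subtract also the average chance that the last two share an arm, (0.333 + 0.400 + 0.429 + 0.455)/4 = 0.40. This leaves 0.13.

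The reductions are 1 − 0.54/2.0 = 73% and 1 − 0.13/0.67 = 81%.

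**Best-guess accuracy (simulation, every arm learned).**

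| L | fixed 10 | varying |
|---|---|---|
| 0 | 65% | 67% |
| 1 | 60% | 60% |
| 2 | 58% | 57% |
| 3 | 56% | 55% |

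**The case against.** The best defence is that the headline figures need staff to learn every arm promptly. Section D says only that awareness may happen, in a contact meant as a reminder, and gives no date for the first one. With half the arms learned, the expected number is close to zero. This stands: 2.0 is the top of a range, not a forecast.

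Second, the envelope is prepared independently, and section F restricts knowledge of the arm to two roles. That protects each participant's own assignment. It does not answer deduction from earlier ones, and the permissions elsewhere contradict the restriction.

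Third, a deducible list position is not yet a particular patient. A physician's eligibility check, consent and a pregnancy test come between approach and continuation, so someone else may take the place. Everyone also receives active stimulation by Week 8, which weakens any motive to steer. Both points reduce the risk without removing it.

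Fourth, varying the block sizes barely changes guessing accuracy and slightly worsens it if every arm is known at once. That is correct. The gain is fewer certain allocations.

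Fifth, the 5:5 split is inferred and the named method is undefined. If the method already implies varying blocks, the text should say so. As written, it says 10.

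**Conclusion.** The point holds as a small, low-cost improvement. With every arm learned and enrolment spread over a year, about 2.0, 0.7 or 0.2 of 30 allocations are expected to be deducible with one, two or three recent arms unknown. If half the arms are learned, the figure is about 0.07 or fewer, and with fast enrolment and disclosure only at Week 4 it is also near zero. The result rests on the inferred 5:5 split, the assumed enrolment period and how much staff actually learn.

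A reader might infer that five of 30 allocations will be known, with the 10th, 20th and 30th always certain, or that concealment has failed and selection will occur. The documents do not support this. Five requires immediate knowledge of every arm, whereas disclosure here is delayed and mostly optional, and nothing in the text shows that anyone would act on it. Nor would varying block sizes make every allocation unpredictable, because the 15:15 total is printed.

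**What to change.** 1. In section O, replace the fixed size with permuted blocks of varying size in random order, totalling 15 per arm. The biostatistician generates the sizes, and only the biostatistician and the independent coordinator know them. Keep the sizes out of the protocol that recruiting staff hold, and say what the named randomization method means.
2. Reconcile the permissions in section D (Week 0) and section F (Week 4 visit) with the section F statement that only two roles know the arm. Reconcile also the two accounts of how the Week 4 instructions are given. This matters because the disclosures are what make deduction possible.

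The cost of the first change is one sentence and a new list for participants not yet randomised. The second is a text edit. The 15:15 split is kept, and no patients or staff are added. The drawback is the slightly higher guessing accuracy (67% against 65%) in the unlikely case that every arm is known at once.

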- **Expected outcome:** Based on prior experience, in more than half the subjects, we expect hfHRV to improve by 10% from baseline to week 4, along with an FDI score improvement of >5 points, and an improvement in the worse 2 symptoms by 2 points.

Aim 2: Pro-inflammatory cytokines drop as assessed by LPS-induced cytokine production

- **Objective 2:** If vagal modulation improves, we expect a decrease in inflammatory cytokine production, particularly TNF α , IL6 and IL8.
- **Expected outcome**: We expect a significant reduction by 10% or more in TNF α (index cytokine) and some reduction in other cytokines as well.

C. BACKGROUND, SIGNIFICANCE, AND RATIONALE

Painful functional gastrointestinal disorders (pFGIDs) affect 10-20% of the pediatric population² and impair daily activity in 40%³, yet studies in children are few^{4,5}. The management has not been standardized as so few interventions show any benefit. These include dietary changes like the FODMAP diet^{6,7}, probiotics⁸, hypnosis and cognitive behavioral therapy⁹⁻¹², peppermint oil¹³ and recently, an auricular neurostimulator¹⁴. This neurostimulator improves abdominal pain¹⁴. For pain, opioids are still too frequently used, despite the absence clear benefit and significant risk of substance use disorder and side effects¹⁵. Furthermore, **opioids are proinflammatory¹⁶**, **worsening the neuro-inflammatory process and the chronic pain syndrome**, and carry a significant risk of substance use disorder. This risk is great in adolescents for several reasons. First, brain immaturity increases the tendency to impulsivity and vulnerability to alcohol and other drugs with long-term behavioral and cognitive dysfunctions. Second, the family setting allows access to opioids from other family members in the household¹⁷. Third, even a few doses of opioids given in the post-operative setting can induce

substance use disorder in adolescents. Finally, having chronic pain as happens in FGID is a risk factor for opioid addiction in itself^{18,19}. Given these facts, it is critical to find a low-risk, effective, non-invasive and accessible treatment that impacts the core pathophysiology of FGID, not just the symptoms.

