1. Functional Disability Inventory (FDI) will be completed by the participant (FDI-Child and Adolescent Form) and his/her parent (FDI-Parent Form). The FDI assesses the functional status of each subject. This brief 15item instrument is widely used to assess functional disability in pediatric samples³⁵, including pediatric pain ^{36,37}. Both self- and parent proxy-reports will be used. The FDI has strong internal consistency (males $\alpha = 0.86$; females $\alpha = 0.91$), reliability, and validity³⁶. Developed and validated by Walker³⁵, the FDI measures daily functions on a 5-point Likert scale such as ambulation, recreation, capacity for social interaction, performing chores, going to school, sleep, and eating. Validated for children with chronic abdominal pain, it shows excellent test-retest reliability within 2 weeks, and moderate at 3 months. It correlates well with school-related disabilities and both the child-report and the parent-report scores correlate with abdominal pain measures and other somatic symptoms^{36,37}.

2. Symptom Intensity Questionnaire score will be used to identify the most prominent 5 complaints rated in a 10 cm Likert scale the intensity form. Patients will write in each of their top 5 most severe symptoms on the corresponding line. They will then rate the symptoms severity from none (0 cm) to worst you can possibly imagine (10 cm) by placing a vertical line on the scale.

3. The Pain Catastrophizing Scale (PCS) will be completed by the participant (PCS-C) and his/her parent (PCS-P). The PCS-C is a modification of the adult Pain Catastrophizing Scale for use in children, measures pain-related cognitions and the dimensions of helplessness, rumination and magnification. This measure has both child-report and parent-report forms³⁸.

4. The Revised Child Anxiety and Depression Scale (RCADS) assesses children grades 3 to 12 containing subscales assessing for symptoms of Separation Anxiety Disorder, Social Phobia, Generalized Anxiety Disorder, Panic Disorder, Obsessive Compulsive Disorder, and Major Depressive Disorder.

5. Participants will be asked to complete the TENS Unit Daily Recording Diary while they are participating in this study. This diary consists of three columns; Date, Time 1, Time 2. Participants will update this diary daily to note when they used the TENS unit.

Blood for cytokines and flow cytometry

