A qualified nurse from the Pediatric Translational Research Unit will collect up to 59ccs (3-4 tablespoons) of blood from each participant at study visit weeks 0, 4, and 8. A member of the research team who has completed laboratory training on the use of the centrifuge and hood, will initially process the blood prior to escorting the sample to [name] lab in coded tubes. Members of [name] lab will not be privy to any PHI. Due to decreased laboratory staffing/resources during Covid-19, samples will be frozen by a member of the research team after initial processing. These samples will remain viable until flow cytometry can be completed can be

	Week 0 Visit	Week 4 Visit	Week 8 Visit
Consent	Х		
Pregnancy Test	Х		
Device Randomization	Х	X	Х
MD Assessment	X	X	
TENS Unit and Auricular Clip Placement	Х	Х	Х
HRV	Х	Х	Х
FDI (Child and Adolescent Form and Parent Form)	Х	Х	Х
Symptom Intensity Questionnaire	Х	X	X
PCS-C	Х	X	X
RCADS	Х	X	
TENS Unit Daily Recording Diary	Х	X	X
Cytokines and Flow Cytometry			

completed by [name] lab. Primary blood mononuclearcells will be isolated by density-gradient centrifugation through Ficol/Hypaque (Pharmacia), suspended (8 ′ 106cellsml-1) in RPMI 1640 medium with 10% heat inactivated human serum (Gemini Bio-Products), and seeded in flasks. After incubation for 2h at 378C, adherent cells will be detached with 10mM EDTA, resuspended (106 cellsml-1) in medium supplemented with human MCSF (Sigma; 2 ngml-1), and seeded onto 24-well tissue culture plates (106cellsper well). Cells will be allowed to differentiate for seven days in the presence of MCSF. On day seven, fresh medium without MCSF will be added. LPS will be added to the cultures at a final concentration of 100ngml-1. Supernatants will be collected 4 and 20h after the addition of LPS and prepared for cytokine analysis. We will ship samples to Eve Technologies (located in Canada) where they will use their assay service to analyze the human cytokine array/Chemokine 42-Plex. We will use the high sensitivity assay due to low levels of cytokines in humans and will evaluate a panel consisting of EGF, Eotaxin-1, FGF-2, Flt-3L, Fractalkine, G-CSF, GM-CSF, GRO(alpha), IFNalpha2, IFNgamma, IL-1alpha, IL-1 beta, IL-1ra, IL-2, IL-3, IL-4, IL-5, IL-6, IL-7, IL-8, IL-9, IL-10, IL-12 (p40), IL-12 (p70), IL-13, IL-15, IL-17A, IL-18, IP-10, MCP-1, MCP-3, MDC, MIP-1alpha, MIP-1beta, PDGF-AA, PDGF-AB/BB, RANTES, sCD40L, TGFalpha, TNFalpha, TNFbeta, VEGF-A.

Pregnancy Test

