The RR-interval time series recorded by the monitor will be detected from surface ECG signals at a sample rate of 1000 Hz and will be downloaded from the devices for further processing using custom HRV analysis software. The heart rate time series will be manually reviewed and processed in segments, excluding those from variability analysis in which artefacts or gaps account for > 15% of the recording. Shorter gaps will be replaced with intervals interpolated from adjacent normal beats. Frequency-domain analysis will be performed after constructing a detrended instantaneous RR-interval time series resampled at 5 Hz by piecewise cubic Hermite interpolation. The absolute and log-transformed power spectrum densities of consecutive segments will be computed for the frequency ranges of 0.04 to 0.15 Hz, designated as low-frequency power (LF), and 0.15 to 0.4 Hz, designated as high-frequency (HF) power. HF fraction will be computed as HF / (LF + HF) in addition to the LF/HF ratio. The HF power has been shown to result predominantly from parasympathetic modulation of heart rate. Time domain HRV parameters will include the standard deviation of all normal sinus beat (NN) intervals and the square root of the mean of the sum of the squares of differences between adjacent NN intervals. In addition to the inspection of the detected RR-intervals provided by the monitor, we will scan the recordings for non-stationary conditions employing Kalman-filter and wavelet-based spectrograms. Statistical analysis will be based on standard parametric or non-parametric group comparisons, as well as correlation computations were appropriate. The agreement between detected beats and the computed parameters for timedomain and frequency-domain HRV analysis between the monitors will be examined using Bland-Altman plots and summarizing using canonical correlations.

P. FINANCIAL RELATIONSHIPS

This study is supported by the 2020 CTSI Traditional Pilot Award. Participants will receive a total stipend of \$70 for participating in this study via check (\$20 after visits 1,2 and \$30 after final visit).

Q. ADVERTISEMENTS / FLIERS

We will not use advertisements or flyers for this protocol.

R. BIBLIOGRAPHY

- 1. Hoekman, D.R., et al., *The Placebo Response in Pediatric Abdominal Pain-Related Functional Gastrointestinal Disorders: A Systematic Review and Meta-Analysis.* J Pediatr, 2017. **182**: p. 155-163.e7.

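### The plan does not say how week 0 values enter the week 4 active-versus-sham comparison, or how arm enters the correlations; naming ANCOVA and an arm-adjusted correlation would settle both.

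*Combined protocol and SAP*

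**What the plan says.** The combined protocol and SAP has one inferential sentence, under Heart Rate Variability in Section O: "Statistical analysis will be based on standard parametric or non-parametric group comparisons, as well as correlation computations were appropriate". The Data analysis overview in the same section adds summary statistics and this rule: "To satisfy parametric assumptions, we may perform transformations with justifications if possible and otherwise use non-parametric tests". Neither place names a covariate, an outcome form (week 4 value, change or percentage change) or the role of arm in a correlation. FDI and cytokines have no analysis text beyond the overview.

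Other sections narrow the reading. Section B sets the contrast as four weeks of active stimulation against sham, and the blinding text in Section F also describes a comparison between the two versions. The Aim 1 expectation is framed as change: "we expect hfHRV to improve by 10% from baseline to week 4, along with an FDI score improvement of >5 points". Aim 1 also seeks a correlation between clinical improvement and the hfHRV rise. Section A would read a high correlation between cytokine inhibition and benefit as a potential mechanism.

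HRV, FDI and cytokines are all collected at week 0 (Sections D and F).

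**The concern.** With 15 patients per arm, the choice between week 4 values, change and ANCOVA can move power noticeably, and the plan leaves it open. ANCOVA needs only data already planned. If week 0 means happen to differ between arms, it is also the only one of the three that keeps its 5% error rate given that difference. The rank-test route in the overview has no adjustment for week 0 either.

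The correlations raise a different issue. If stimulation raises hfHRV and separately improves FDI, the two changes correlate across all 30 patients even when patients with larger hfHRV rises do no better than others in their own arm. Such a correlation partly repeats the two arm effects, yet it could be read as evidence of mechanism.

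**Working it through.** **Inputs from the documents.** 30 patients, 15 per arm (Section D); randomisation in blocks of 10 (Section O). Section O mentions a power calculation, but the documents give none of its inputs or results, so the figure of 30 cannot be reproduced.

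**Assumptions.** Two-sided 5%, no dropout, normal outcomes, true difference d of 0.8 or 0.5 SD, rho from 0 to 0.8.

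**Group comparison.** Variance relative to a comparison of week 4 values alone:

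- change score: f = 2(1 − rho)
- ANCOVA: f = (1 − rho²)(1 + 1/26), where 1/26 is the expected cost of estimating the slope

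The noncentrality is d / √(f × 2/15), with 28 df (27 for ANCOVA). For example, at rho 0.5 and d = 0.8:

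- change: f = 1.00, 0.8/0.365 = 2.19, power 56%
- ANCOVA: f = 0.75 × 1.038 = 0.779, 0.8/0.322 = 2.48, power 67%

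| rho | f, change | f, ANCOVA | Power at 0.8 SD: week 4 / change / ANCOVA | Gain over change (points) | Power at 0.5 SD: change / ANCOVA | Gain (points) |
|---|---|---|---|---|---|---|
| 0 | 2.00 | 1.038 | 56 / 32 / 55% | 22 | – | – |
| 0.3 | 1.40 | 0.945 | 56 / 43 / 58% | 15 | 20 / 27% | 7 |
| 0.5 | 1.00 | 0.779 | 56 / 56 / 67% | 11 | 26 / 32% | 6 |
| 0.7 | 0.60 | 0.530 | 56 / 78 / 83% | 5 | 40 / 44% | 4 |
| 0.8 | 0.40 | 0.374 | 56 / 92 / 93% | 1–2 | 55 / 58% | 3 |

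Simulation agrees with the 0.8 SD columns. To match ANCOVA at 0.8 SD, change scores would need 22, 19, 17 and 16 per arm at rho 0.3, 0.5, 0.7 and 0.8. The worst case for ANCOVA is rho 0, where it loses 56.2 − 54.6 = 1.6 points to week 4 values.

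**Chance imbalance.** The difference in week 0 means has SD √(2/15) = 0.365, so it reaches 0.5 SD in about 17% of trials. In those trials, with no treatment effect and rho 0.3/0.5/0.7/0.8, change scores reject in 14/11/9/8%, week 4 values in 7/11/18/22%, and ANCOVA in 5%. Averaged over all randomisations, all three hold about 5%.

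**Correlation.** If both changes shift by d within-arm SDs between arms and the within-arm correlation is r, the pooled correlation is (r + d²/4)/(1 + d²/4). For r = 0 and d = 0.8 that is 0.16/1.16 = 0.14; for r = 0.3 it is 0.46/1.16 = 0.40. Simulated rejection rates:

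| Shift in both measures (SD) | r = 0: pooled r | r = 0: rejection, pooled / adjusted | r = 0.3: rejection, pooled / adjusted |
|---|---|---|---|
| 0.5 | 0.06 | 6 / 5% | 47 / 36% |
| 0.8 | 0.14 | 11 / 5% | 61 / 36% |
| 1.0 | 0.20 | 19 / 5% | 72 / 36% |
| 1.5 | 0.36 | 54 / 5% | 93 / 36% |

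With unequal shifts and r = 0, the pooled rate is 6% (0.3 and 0.8 SD) or 9% (0.5 and 1.0 SD). With no shift, the lost degree of freedom costs little: at r = 0.3, 37% pooled and 36% adjusted.

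**The case against.** A reader might infer that the planned analyses ignore week 0 values and arm. The documents do not support that. The group comparisons are by arm, and the Section B expectations point to change from baseline. Nor does any section say that the arms will be pooled in the correlations. The plan is silent on both.

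It can also be argued that ANCOVA offers little here. Against change scores the gain is only 1 to 2 points at rho 0.8, and it is roughly halved at rho 0.3 and 0.5 if the true difference is 0.5 SD. For FDI, Section F reports that "it shows excellent test-retest reliability within 2 weeks, and moderate at 3 months". This suggests a fairly high rho at four weeks and a gain toward the lower end. Nothing comparable is given for hfHRV or TNF-alpha. This objection limits the size but does not remove the gain.

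The Randomization text, "The sample size in this pilot study is small and it would likely result in bad imbalance of the two groups", is weak support. It most naturally explains why blocking is used and does not mention week 0 values. It remains true that blocks balance numbers per arm, not week 0 values.

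The strongest objection concerns the correlation. Arm adjustment is not a nearly free gain. It answers a narrower question and removes the between-arm part that a mediated effect would also produce. Under the study's own hypothesis, where both measures respond to treatment, rejection can fall substantially. That stands, and it is why the pooled value should be kept beside the adjusted one.

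**Conclusion.** The point holds as a gap in specification with a better method available. The plan does not say whether or how week 0 values enter the week 4 comparison, or how arm enters the correlations. ANCOVA would gain about 15, 11, 5 and 1 to 2 points over change scores at 0.8 SD, and about 7, 6, 4 and 3 at 0.5 SD, for rho 0.3, 0.5, 0.7 and 0.8. These figures rest wholly on assumed alpha, effect and rho.

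It would be wrong to conclude that the present wording makes the group comparison biased: week 4 values, change and ANCOVA are all valid averaged over randomisations. The correlation point is about interpretation, not power. If the arms were pooled, the excess of significant results would be small for modest shifts (6% at 0.5 SD) and serious only for large ones (54% at 1.5 SD).

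**What to change.** **Main comparison.** For log HF power, FDI and log TNF-alpha, name ANCOVA as the deciding analysis: week 4 value on arm plus the week 0 value of the same measure. Fix each measure in advance:

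- the posture for HF, since "We will measure vagal modulation supine and standing utilizing heart rate variability"
- the LPS time point for TNF-alpha, since "Supernatants will be collected 4 and 20h after the addition of LPS"
- the child or parent form for FDI

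Report the adjusted difference with its 95% CI. On the log scale it back-transforms to an active/sham ratio. That is not the within-subject 10% change expected in Section B and should not be presented as a test of it.

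**Sensitivity analysis.** Name rank ANCOVA (ranks of week 4 on arm and ranks of week 0) in place of an unadjusted rank test, and state that it does not decide.

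**Correlations.** For Aim 1, and for TNF-alpha if the Section A mechanism conclusion is to be drawn, report the arm-adjusted partial correlation of week 0 to week 4 changes with its CI, beside the pooled value and the two arm-specific estimates. Base within-patient mechanism statements on the adjusted value, and call them non-randomised evidence that does not prove mediation. State the cost: about 61% to 36% rejection at within-arm r = 0.3 and 0.8 SD shifts. Precision is limited by n = 30, not by the adjustment: an observed r of 0.4 has a 95% CI of 0.05 to 0.66 unadjusted and 0.04 to 0.67 adjusted. Within one arm it is −0.14 to 0.76, so those estimates are descriptive.

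**Symptom scores.** Do not limit symptom models to symptoms rated at both visits. Section F says "Patients will write in each of their top 5 most severe symptoms on the corresponding line", so a symptom that improves may leave the week 4 list, and the restriction would select on a post-randomisation outcome.

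**Cost.** A few lines of SAP text, no new data, and one degree of freedom per adjustment. For ANCOVA that is at most about 2 power points, at rho 0.
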